8.4 Handling of Dropouts or Missing Data

Safety analyses will be performed based on all available data.

Analyses on ALS-FRS, SVC [REDACTED] will primarily be based on available data (without imputation). To assess the robustness of results, multiple imputations will be used for analyses on these endpoints. More details are given under the analysis plan for each endpoint in Section 10.

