Descriptive statistics on the observed and change from baseline in the ALSFRS-R total score, ALSFRS-R motor score, and SVC will be summarized at each visit, by treatment group. The analyses will be evaluated for the FAS primarily based on available data (no imputation). Figures presenting the mean ALSFRS-R total and motor scores and SVC score over time by treatment group will be presented. Additionally, figures presenting the ALSFRS-R total and motor scores over time, as separate line plots for each subject will be generated. The change from the Screening Visit measure will be summarized for measures during pre-transplantation. The change from Baseline measure will be summarized for measures post-transplantation. The pre-transplantation slope (change in score per month calculated as the difference between the visit date minus the screening date divided by 30.4375) will be estimated from visits prior to transplantation (including the measure pre-transplantation at the transplantation visit). The post-transplantation slope (change in score per month calculated as the difference between the visit date minus the transplantation date divided by 30.4375) will be estimated from visits post transplantation (including the measure pre-transplantation at the transplantation visit). The analysis of change in slope from pre-transplantation to post-transplantation in ALSFRS-R total and motor and in SVC will be estimated using a two-step model. In the first step, linear regressions will be fitted to each subject's pre-transplantation and post-transplantation data separately; and in the 2nd step, the slopes (pre- and post-transplantation slopes) from the first step will be used as a response variable and treatment, period (0 for pre-transplantation slope and 1 for post-transplantation slope), and treatment by period interaction as explanatory variables in a fixed-effects linear model. The two-way interaction between treatment and period will be used to compare the change in slope

in the active treatment group to the change in slope in the placebo group. The post - pre slope estimate within each treatment group will be used to test the change from pre-transplantation to post-transplantation.

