The slopes, pre- and post- transplantation and the difference in slopes pre- and post-transplantation will be tested for normality using the Kolmogorov-Smirnov statistic. If the slopes deviate from normality additional summaries will be presented using a Wilcoxon Rank-Sum test on the slope estimates obtained from the mixed-effects linear model. The above analysis is based upon all data from screening through Week 24 and similar analysis will be repeated through 8-week, 12-week, 16-week follow-up periods for ALSFRS and through 8-week and 16-week follow-up periods for SVC.

To assess the robustness of the analysis results when warranted, the two-step model will be repeated with missing values imputed using multiple imputation methods. The monotone regression method will be performed using the SAS procedure PROC MI.

Note, that repeating the imputation 30 times allows for a better understanding of the additional variability inherent in imputing missing values. ALSFRS-R motor scores will be calculated similarly. The 30 sets each of total and motor ALSFRS-R scores will then be analyzed by standard SAS mixed modeling method as specified earlier. [REDACTED]

The procedure for imputing for SVC is analogous to ALSFRS-R. Again, 30 complete datasets will be generated and the Linear Mixed Model to analyze SVC will be fitted on each of the 30 datasets and the results combined to give yield overall inference.

Each subject's pre and post-treatment slope, standard error, and p-value testing the slope versus 0 will be presented in a listing. Additionally, the percent change in slope (post – pre)/absolute(pre) will be calculated and listed. The frequency and percentage of subjects with at least a 10%, 15%, 20%, 25%, and 30% change (improvement) in slope will be summarized and tested between the treatment groups using Fisher's Exact test. These analyses will be performed for subjects showing improvements in ALSFRS-R, SVC, ALSFRS-R and SVC, ALSFRS-R or SVC over the 8-week, 16-week and 24-week post-transplantation follow-up periods.

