showing changes in suicide ideation scores from screening (lifetime measure) to worst on Baseline (pre-transplantation period) and from Baseline to worst post-treatment will also be provided. Data will be reported as available without data imputation.

12. Interim Analyses

There are no interim analyses planned for this study.

13. Deviations from Protocol-Stated Analyses

- [REDACTED]
- [REDACTED]
- [REDACTED]
- Updated mixed linear repeated measures statistical model to be a simple linear regression along with general linear model to compare changes in slopes between treatment groups as described above.
- Added slope analysis for 8-week and 16-week follow-up periods was added for the efficacy endpoints.
- Changed population definitions from the protocol stated definitions by removing analyses on mFAS and PP populations.
- Protocol referred to day of transplantation as Day 0, however in the SAP it is treated as Day 1.
- Changes between the original protocol and Amendment 1 are assumed to not impact any statistical analyses

14. Reporting Conventions

Reporting conventions will adhere when possible to the International Conference on Harmonization (ICH) Guidance E3, "Structure and Content of Clinical Study Reports". All tables and listings will be presented in landscape format. All SAS output for tables and listings will be distributed in PDF files.

15. References

16. SAP Revision History

Section #	Description of Change	Rationale
6	Updated FAS definition and removed mFAS	During the blinded data review it was determined that the difference between the FAS and mFAS was only one subject and hence no analyses would be performed on the mFAS

Section #	Description of Change	Rationale
6	Analysis on PP population is deleted	Due to the small sample size in the study, the 3:1 ratio of randomization between active and placebo and the possibility that a disproportionate number of the subjects may be in the Placebo group, analysis on the PP population will not be performed.
10.2 and 10.3.1	Updated the primary model from mixed-effects linear model to two-step model.	The mixed-effects linear model has restriction on the random effects estimates (slope) which causes the estimated slopes to be either lower or higher than the actual slopes from simple linear regression which was deemed to be more appropriate.

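### SAP 10.2 adopts a two-step slope analysis, but takes the fallback Wilcoxon slopes from an unspecified mixed model and names both models for the imputed data

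*SAP*

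**What the plan says.** SAP Section 10.2 states that change in slope for ALSFRS-R total, ALSFRS-R motor and SVC "will be estimated using a two-step model". Step one fits ordinary regressions to each subject's pre- and post-transplantation data separately. Step two puts those slopes into a fixed-effects linear model with treatment, period and their interaction. Neither step is a mixed model. SAP Section 13 records the switch: "Updated mixed linear repeated measures statistical model to be a simple linear regression along with general linear model".

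Two later instructions in Section 10.2 do not follow this:

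- **Non-normal slopes.** Pre slopes, post slopes and their difference are tested for normality. If they fail, "additional summaries will be presented using a Wilcoxon Rank-Sum test on the slope estimates obtained from the mixed-effects linear model".
- **Imputed data.** The text opens with "the two-step model will be repeated with missing values imputed using multiple imputation methods". It then says the 30 sets of ALSFRS-R total and motor scores "will then be analyzed by standard SAS mixed modeling method as specified earlier", and for SVC that "the Linear Mixed Model to analyze SVC will be fitted on each of the 30 datasets".

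SAP Section 8.4 gives the reason for imputing, "To assess the robustness of results, multiple imputations will be used for analyses on these endpoints", and sends the reader on for the method: "More details are given under the analysis plan for each endpoint in Section 10".

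**The concern.** One analysis has been given two models. A programmer following Section 10.2 literally would compute the main result from per-subject regression slopes, the non-parametric check from slopes of a different and unspecified model, and the imputed results from either model.

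Two things are at stake. First, if the imputation run changes the model as well as the handling of missing values, a different answer cannot be attributed to missing data, and the run loses most of its value as a robustness check. Second, the Wilcoxon result would depend on a mixed model that someone must choose later. SAP Section 16 says the mixed model was dropped because its slopes come out lower or higher than the simple-regression slopes, which were judged more appropriate. The Wilcoxon sentence would rank the slopes that were set aside.

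**Working it through.** **Text comparison**

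| Analysis | Model named in SAP 10.2 |
|---|---|
| Main, available data | Two-step |
| Wilcoxon if non-normal | Mixed-effects model |
| Imputed data, opening sentence | Two-step |
| Imputed ALSFRS-R total and motor | Mixed modelling, said to be already specified |
| Imputed SVC | Linear mixed model |

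The only mixed model spelled out for these endpoints is in protocol Section 6.9.4.3. It lists fixed effects and a residual covariance structure chosen by BIC, with no random slope. As written it yields no per-subject slopes to rank.

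**Inputs for the illustration**

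The plan has no figure of its own to reproduce here. From the documents: 36 and 12 subjects (SAP Section 5), one-sided alpha 0.10 (SAP Section 8), and the visit schedule. Assumed: pre-transplantation visits at weeks -14, -9, -5 and 0 (mid-window); ALSFRS-R at weeks 2, 4, 8, 12, 16, 20 and 24, and SVC without weeks 12 and 20; between-subject slope SD 0.5 to 1.5 points/month; pre/post slope correlation 0 to 0.8; residual SD 0.5 to 1.5; intercept SD 5; mean decline 1 point/month; complete data. There were 10 scenarios of 4,000 replicates.

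**1. Changing the model in the imputation run**

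Each model estimates a subject's slope change as a weighted sum of that subject's scores. The two-step weights come from separate pre and post regressions that both include day 0. The mixed-model weights come from two lines joined at day 0, as in the protocol's time terms. On complete balanced data this holds for a random-slope model or for the protocol's compound-symmetry option.

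SD of shift = residual SD × ‖w(two-step) − w(mixed)‖ × √(1/36 + 1/12), where √(1/36 + 1/12) = 0.3333.

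| Window | SD of shift ÷ residual SD |
|---|---|
| ALSFRS-R, Week 24 | 0.2409 × 0.3333 = 0.0803 |
| ALSFRS-R, Week 16 | 0.0726 |
| ALSFRS-R, Week 12 | 0.0708 |
| ALSFRS-R, Week 8 | 0.0858 |
| SVC, Week 24 | 0.0791 |

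For residual SD 0.5 to 1.5, Week 24 gives 0.0803 × 0.5 = 0.04 to 0.0803 × 1.5 = 0.12 points/month. The median shift is 0.04 to 0.30 of the two-step standard error when step two is paired within subject. With that pairing, so that only the slope model differs, the one-sided 0.10 verdicts disagree in 0.9% to 6.7% of trials under no effect, and in 1.2% to 14.9% under an assumed effect of 0.3 to 0.5 points/month. The SAP's step two does not state the pairing; it is used here to keep that separate issue out of the comparison.

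**2. Wilcoxon test on mixed-model slopes**

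Predicted slopes are pulled toward a mean. Ignoring the correlation between pre and post slopes, the factor is τ²/(τ² + σ²/Sxx), where τ is the slope SD, σ the residual SD and Sxx the spread of visit times in months². Sxx is 5.61 before transplantation, 28.32 after it to Week 24, and 1.85 to Week 8. With τ = 0.5 and σ = 1.0 the factors are:

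- pre: 0.25/(0.25 + 1/5.61) = 0.58
- post to Week 24: 0.25/(0.25 + 1/28.32) = 0.88
- post to Week 8: 0.25/(0.25 + 1/1.85) = 0.32

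If the model contains treatment terms, slopes shrink toward their own arm's mean. Within-arm spread falls while the chance difference between arms stays, so the rank test rejects too often. Simulated error at Week 24, ranking the post-minus-pre change:

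| Slope SD, correlation, residual SD | Mixed, treatment terms | Mixed, no treatment terms | Step-one slopes |
|---|---|---|---|
| 1.5, 0, 0.5 | 0.106 | 0.104 | 0.104 |
| 1.0, 0.5, 1.0 | 0.139 | 0.097 | 0.102 |
| 1.0, 0.8, 1.0 | 0.193 | 0.104 | 0.105 |
| 0.7, 0.8, 1.5 | 0.330 | 0.102 | 0.093 |
| 0.5, 0.8, 1.0 | 0.315 | 0.093 | 0.101 |
| 0.5, 0.8, 1.5 | 0.363 | 0.098 | 0.096 |

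These use estimated variance components. Across all scenarios at Week 8 the ranges are 0.113 to 0.388 (treatment terms), 0.095 to 0.106 (none) and 0.091 to 0.104 (step-one slopes).

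**The case against.** The strongest reply is that this is leftover wording after a declared change of model, in analyses that matter little. The opening imputation sentence names the two-step model, the ALSFRS-R sentence points back to whatever came before, and the SVC procedure is described as analogous. The endpoints are secondary in a Phase 2 safety study with no formal sample size.

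Much of that stands. The leftover reading is natural for ALSFRS-R and possible for SVC, though the SVC sentence names a linear mixed model outright. A redacted block follows the ALSFRS-R sentence and may hold details of that analysis or of pooling. It cannot remove the visible conflict in the Wilcoxon and SVC sentences. SAP Section 16 mentions random-effect slope estimates, so a random-slope model was evidently in mind, but the readable text never specifies it. Section 8.4 speaks of robustness in general; that the run should isolate missing-data effects is an inference from the section's subject.

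The numerical caveats also stand. The high error rates need treatment terms in the model and arise in noisy, highly correlated settings. The simulation omits the normality trigger. In a separate check assuming a 0.05 Lilliefors-type trigger, normal slopes triggered in about 14% of runs, and the inflation, where present, largely persisted among them. The trigger therefore limits how often the problem arises without removing it.

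**Conclusion.** The concern holds. It rests on the wording of Section 10.2, not on the simulations. The Wilcoxon instruction cannot be carried out without supplying a model that the readable plan lacks, and the imputed datasets have two models assigned to them.

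The scope is narrow: a conditional supplementary test and a sensitivity run made only when judged warranted. Within it, the choice of model can matter. Under the assumptions listed, a model switch alone can reverse up to about 15% of verdicts at Week 24. The Wilcoxon error ranges from nominal to more than three times nominal (0.363/0.10 = 3.6), depending on which mixed model is supplied. The documents give no variance components, so these figures show what is possible rather than what to expect. It should be fixed before analysis, but it does not put the main result in doubt.

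**What to change.** Make three changes to SAP Section 10.2:

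1. Run the Wilcoxon test on the step-one regression slopes, with each subject's post-minus-pre difference as the treatment comparison. Summarise pre and post slopes the same way where they are non-normal, since all three are tested for normality.
2. Replace both mixed-model references in the imputation text with one statement: each of the 30 imputed datasets for ALSFRS-R total, ALSFRS-R motor and SVC is analysed with the same model as the main analysis, and the results are combined across imputations.
3. If a mixed-model sensitivity analysis is wanted, give its fixed effects, random effects and covariance structure, label it as separate, and run it on the observed data too, so that the effects of model and imputation can be told apart.

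The first two follow the sponsor's own declared choice of model; the third is optional. The cost is wording only, with no effect on data, sample size or timing.

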10.2.1 Subgroup analyses

Subgroup analyses will be performed to investigate the consistency of the treatment effects for different groups of subjects.

Subgroup analyses will be conducted for the following endpoints:

- ALSFRS-R total score
- ALSFRS-R motor score
- SVC

Subgroups to be evaluated include the following:

- Baseline SVC:
 - $\geq 70\%$
- Baseline ALSFRS-R total score:
 - < -2 in the change from screening to baseline in ALSFRS-R total score
 - ≥ -2 in the change from screening to baseline in ALSFRS-R total score
- Baseline ALSFRS-R motor score:
 - < -1 in the change from screening to baseline in ALSFRS-R motor score
 - ≥ -1 in the change from screening to baseline in ALSFRS-R motor score

The primary analysis model will be repeated for each level of the subgroups.

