7.2 Efficacy Endpoints

The efficacy endpoints are the following:

- Revised ALS Functional Rating Scale (ALSFRS-R)
- Slow Vital Capacity (SVC) (as a percent of normal)

[REDACTED]

[REDACTED]

[REDACTED]

[REDACTED]

[REDACTED]

[REDACTED]

8. General Considerations

Summaries for continuous variables will include the sample size, mean, standard deviation, median, minimum, and maximum. Minima and maxima will be reported with the same precision as the raw values; means, standard deviations, and medians will be presented to one additional decimal place than reported in the raw values. Summaries for discrete variables will include frequencies and percentages. All percentages will be rounded to one decimal place (i.e., XX.X%). Differences between treatment groups will be calculated as active – placebo and change from Baseline will be calculated as post-treatment – pre-treatment (OR follow-up visit – Baseline). The Baseline value will be defined as the last non-missing measure prior to initiation of investigational treatment. Additionally, for the pre-transplantation period and Transplantation Visits, change from screening summaries will be calculated as pre-transplantation period/Transplantation Visit minus screening.

All efficacy analyses will use one-sided alpha = 0.10 tests (which corresponds to a 2-sided alpha=0.20 test). The two-sided 80% lower confidence limit will be presented for which the lower bound is the 1-sided 90% confidence limit. In addition, the two-sided 90% and 95% confidence intervals around the difference between treatments as well as two-sided 95% confidence intervals around the point estimates within each treatment group will be provided. All summaries will be presented by treatment.

Statistical programming and analyses will be performed using SAS® Version 9.2 or higher.

[REDACTED]

[REDACTED]

[REDACTED]

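### In subgroups cut on screening-to-baseline ALSFRS-R change, within-arm post-minus-pre slope results for ALSFRS-R carry regression to the mean; the active-minus-placebo contrast does not, but it is imprecise (minor)

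*SAP*

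**What the plan says.** SAP 10.2.1 gives the purpose: "Subgroup analyses will be performed to investigate the consistency of the treatment effects for different groups of subjects". Two of the subgroup factors are cut on change between screening and baseline: ALSFRS-R total (below -2, or -2 and above) and ALSFRS-R motor (below -1, or -1 and above). The first total-score level reads "< -2 in the change from screening to baseline in ALSFRS-R total score". Then: "The primary analysis model will be repeated for each level of the subgroups".

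SAP 10.2 describes that model. Each patient's pre- and post-transplantation slopes come from separate regressions and enter a fixed-effects model with treatment, period and their interaction. The interaction compares the arms. In addition, "The post - pre slope estimate within each treatment group will be used to test the change from pre-transplantation to post-transplantation". The pre-slope "will be estimated from visits prior to transplantation (including the measure pre-transplantation at the transplantation visit"); the post-slope "will be estimated from visits post transplantation (including the measure pre-transplantation at the transplantation visit").

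SAP section 8 (General Considerations) adds: "The Baseline value will be defined as the last non-missing measure prior to initiation of investigational treatment". On testing it says: "All efficacy analyses will use one-sided alpha = 0.10 tests (which corresponds to a 2-sided alpha=0.20 test"). The same section provides two-sided 95% confidence intervals around the estimates within each arm.

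**The concern.** Screening is Visit 1 and baseline is normally the pre-dose value at Visit 5, so the subgroup variable is V5 minus V1. The same two scores are the ends of the four-visit pre-slope (V1, V2, V3, V5), and V5 is also the first point of the post-slope. A patient whose V1 happens to be scored high and V5 low is pushed into the faster-declining level, gets a pre-slope that is too steep and a post-slope that is too shallow, and so appears to improve after transplantation. The reverse happens in the other level.

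A reader of the subgroup tables could then see a significant within-arm slowing among fast progressors, and none among slow progressors, and take it for a treatment effect confined to fast progressors. Printing placebo alongside does not protect the reader. With 36 against 12 patients, placebo often misses significance where active reaches it, although the bias is the same in both arms.

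**Working it through.** **Plan's own figures.** The plan gives no power, SD or precision figure for efficacy or for subgroups. Its only derived probability is the adverse-event figure in SAP section 5, which reproduces (1 - 0.92^36 = 0.950) but has no bearing here.

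**Inputs from the documents.** 36 active and 12 placebo patients; a pre-period of 12-16 weeks; post visits at weeks 2, 4, 8, 12, 16, 20 and 24; reported decline 0.92 to 2.35 points/month (Protocol 6.3.7); one-sided alpha 0.10; 30.4375 days per month, so 30.4375/7 = 4.348 weeks.

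**Assumptions, not in the documents.** Pre visits at weeks -14, -9, -5, 0; linear decline with no true slope change in anyone; between-patient slope SD 0.5-1.0 points/month; residual SD 1-2 points.

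**Step 1, regression weights** (deviation of visit time from the mean time, divided by the sum of squared deviations, times 4.348).
- Pre-slope: mean week -7, sum of squares 106. V5 weight 7/106 x 4.348 = +0.287; V1 weight -0.287.
- Post-slope through Week 24: mean week 10.75, sum of squares 535.5. V5 weight -10.75/535.5 x 4.348 = -0.087.

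**Step 2, one patient.** Constant true slope, V1 one point too high and V5 one point too low.
- Error in pre-slope: -0.287 - 0.287 = -0.574. Error in post-slope: +0.087.
- Post minus pre: +0.66 points/month, and the patient moves 2 points towards the below -2 level.
- With a 12-week pre-period the weight is 0.326 and the result +0.74; with 16 weeks, 0.256 and +0.60.
- Through Week 8 only (weeks 0, 2, 4, 8), the post weight of V5 is -3.5/35 x 4.348 = -0.435 and the result 0.574 + 0.435 = +1.01.

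**Step 3, overlap of cut and pre-slope.** The correlation between error in V5 - V1 and error in the pre-slope is (14/106)/sqrt(2/106) = 0.96 (0.95 for 12 weeks, 0.97 for 16). This needs no SD.

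**Step 4, size in a central case.** With D = V5 - V1, false change in a level = Cov(D, post - pre)/Var(D) x mean deviation of D in that level. Take decline 0.92, slope SD 0.75, residual SD 1.5.
- 14 weeks = 3.22 months; mean D = -0.92 x 3.22 = -2.96.
- Var(D) = 0.75^2 x 3.22^2 + 2 x 1.5^2 = 5.83 + 4.50 = 10.33; SD 3.21.
- Cov = -(0.287 + 0.287 + 0.087) x 1.5^2 = -1.49; ratio -0.144.
- Scores are whole numbers, so the cut lies at -2.5: z = 0.14, with 0.557 of patients below.
- Mean deviation below: -3.21 x 0.395/0.557 = -2.28; above: +3.21 x 0.395/0.443 = +2.86.
- False change: +0.33 below the cut, -0.41 above.

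**Step 5, null simulation of the two-step model** (36:12, integer scores, Week 24). The central case gives about +0.34 and -0.43. Over the assumed SD grid:

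| | Decline 0.92 | Decline 2.35 |
|---|---|---|
| False change, below -2 | +0.14 to +0.58 | +0.01 to +0.15 |
| False change, -2 and above | -0.18 to -0.74 | about -0.4 to -1.6, where estimable |
| Active arm rejects for slowing, below -2 | about 10% to 96% | 0% to 21% |

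At 0.92 the same active-arm test without splitting rejects in 0% to 7% of trials: the model has no patient term and is conservative. In the central case it rejects in about two thirds of trials below the cut, against 2% unsplit, and active is significant with placebo not in about 45%. Within-arm 95% intervals there exclude zero in the false direction in about 31% of trials below the cut and 44% above, against 2.5% nominal.

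**Step 6, the between-arm contrast.** At 0.92 its null mean in the levels is -0.02 to +0.01 and it rejects in 1% to 9%. About 5-7 placebo patients fall in each level, and the two-sided 80% interval half-width is 0.37-0.75 points/month below the cut and 0.42-0.80 above. At 2.35 about 0-1 placebo patients fall at -2 and above, and at least two per arm occurs in only 0% to 40% of trials.

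**The case against.** The strongest reply is that the premise is inferred. SAP 10.2.1 does not list within-arm tests or intervals by subgroup. Its stated purpose, consistency of treatment effects, is served by the treatment-by-period interaction, which is unbiased. That stands as a reason to rate the point low. It does not remove the point, because the model is repeated without restriction and SAP 10.2 makes the within-arm test part of its use.

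Second, the size is not established. At decline 0.92 the rejection rate runs from about nominal to near certain. Protocol 6.9.2.1 gives item test-retest reliability above 0.88. If item SDs were 0.8-1.0 and item errors independent (both assumed), total-score error SD would be at most sqrt(12 x 0.12) x 0.8 to 1.0, about 1.0-1.2, towards the low end of the range used. Scatter about a fitted line can be larger, so this is no bound. At residual SD 1 the rejection rate is about 67%, 28% and 10% for slope SD 0.5, 0.75 and 1.0. The size is therefore a range; the direction is unaffected.

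Third, true slopes may drift. Then part of the apparent change is real, though still not a treatment effect. At decline 0.92, slope SD 1, pre/post slope correlation 0.5 and residual SD 1, an apparent +0.47 includes +0.33 of true change.

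A reader might go further and infer that the subgroup treatment comparison is itself biased. The documents do not support that. Randomization is at Visit 3, before V5, but the V5 score is taken before dosing, so the cut uses only pre-treatment values and the bias is common to both arms. A reader might also infer harm to the trial's main conclusions. The within-arm secondary objective is stated for all patients, unsplit (SAP 2.2); safety is primary; and the criterion for going on to Phase III is against concurrent placebo (Protocol 6.3.7).

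**Conclusion.** The point holds, as a minor one. Within-arm post-minus-pre results for ALSFRS-R slopes, in subgroups cut on screening-to-baseline ALSFRS-R change, are biased towards slowing in the faster-declining level and towards worsening in the other. That direction follows from the SAP's own construction and any non-zero visit error.

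The magnitudes rest on the assumed SDs and on the decline rate. At 2.35 points/month the bias nearly vanishes below -2 but grows in the small level at -2 and above, in the few trials where that level can be estimated. If the subgroups are also run over the shorter windows in SAP 10.2, the bias in points/month is larger: about +0.52 below the cut through Week 8 in the central case.

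The motor-score cut has the same structure, but the documents give no motor decline rate, so no size is claimed. Nothing is claimed about SVC slopes or the baseline SVC subgroup. The consequence is confined to how the subgroup tables are read.

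**What to change.** Add to SAP 10.2.1:

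> For subgroups defined by screening-to-baseline change in ALSFRS-R total or motor score, inference on ALSFRS-R total and motor slopes, at every follow-up window analysed, uses only the active-minus-placebo change-in-slope contrast. Within-arm post - pre estimates in these subgroups are shown descriptively, without p-values or confidence intervals, and labelled as subject to regression to the mean.

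Intervals must be named as well as p-values, because SAP section 8 provides them separately and an interval excluding zero carries the same false message.

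The change is wording only, with no new data, model or term. It gives up within-arm subgroup inference, which cannot be interpreted as a treatment effect. What remains is imprecise, with about 5-7 placebo patients per level at decline 0.92, and may not be estimable at -2 and above if decline is fast. The subgroup tables should say so.
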